A plethora of indices and tools have been studied and marketed to assess intravascular volume status with only a few proven reliable with reproducible results. Based on pre-fluid challenge values, several of these tools have been used to predict who may benefit from additional fluid (fluid responders). Alternatively, some of these tools have been used to distinguish fluid responders from non-responders based on changes in pre- and post-fluid challenge values. Among these tools, the pulmonary artery catheter provides measurements of both left and right heart pressures which can be applied to calculate the cardiac output (CO) and stroke volume (SV). Changes in these values (e.g. an increase in the stroke volume by 10%) between pre- and post-fluid challenge have been used to define fluid responders. This devise, however, is invasive with several significant risks, and therefore is rarely used in children. Echocardiography, on the other hand, is a non-invasive bedside study also used to assess CO and SV but is expensive and requires trained echosonographers for application. Further, because a transthoracic probe is required to obtain the images, application in the operating room is difficult as the chest is often in the operating field limiting access to the echosonographer. Lastly, the esophageal aortic blood flow device (CardioQ-EDM, Deltex Medical, Chichester, UK) has been found in multiple adult and pediatric studies to reliably distinguish fluid responders from non-responders intensive care unit (ICU) and operating room [2-6]. Much like an orogastric tube, this device is simply placed by a provider in the patient's esophagus and uses Doppler waveforms to measure aortic blood flow velocities (**Figure 1**). Variations in the amplitude of peak velocities has been shown to corelate with intravascular volume status[2-6]. Specifically, a change in the peak velocity by greater than 10% between pre- and post-fluid challenge values has

Protocol #: 18-2513

[figure not shown]
PI: [name]

Version date: 07/01/2019

[figure not shown]
been shown to accurately distinguish those who are fluid responsive from those who are not with similar accuracy to echocardiography and pulmonary artery catheter readings[7].

Figure 1

A

B

Legend: A) Illustration of CardioQ-EDM position. In children age 15 years and younger, the device is introduced through the oral cavity. B) Correct placement confirmed by descending aortic waveform.

In recent years with continued technological advancements, there has been enthusiasm about less invasive, and in some cases, non-invasive, tools to gauge volume status. Among these, bedside ultrasonography (performed by providers rather than sonographers) is a common tool used to evaluate the inferior vena cava (IVC) collapsibility index (CI) has been shown to be a reliable tool in adults [8]. Another non-invasive device uses a photoplethysmographic probe (CipherOx-CRI) placed on a digit to calculate the compensatory reserve index (CRI), a marker of proximity to hemodynamic collapse [9]. Both IVC CI and CRI have been shown in multiple adult studies to predict the need for volume expansion, but their utility in the pediatric population is unknown.

The goal of this proposed study is to employ the CardioQ-EDM probe to define fluid responders from non-responders among infants undergoing cranial vault reconstruction for craniosynostosis. After defining these two groups in this single arm prospective trial, we will compare the predictive utility of non-invasive devices such as the CipherOx-CRI and IVC CI to currently employed indices (heart rate, systolic blood pressure, urine output and pulse pressure variability) to gauge the need for additional fluid and ongoing resuscitation. If the CipherOx-CRI or IVC CI proved to be as predictive or better at predicting fluid responders, we hope to replace invasive arterial lines with non-invasive tools to guide resuscitation.

We chose this population for several reasons. First, CHCO performs approximately 50-70 of these cases a year making them a relatively accessible group. Second, these children are generally healthy

Protocol #: 18-2513

PI: [name]

Version date: 07/01/2019

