Hypothesis II: CRI and collapsibility index will reliably predict fluid responsive patients with an approximate area under the receiver operating characteristic curve (AUROC) of 0.9 while other indices will have a lower predictive accuracy.

Aim III: Evaluate confounding variables that may influence predictive measures outlined in Aim II.

Hypothesis III: Confounding variables that may decrease the predictive accuracy of indices described in Aim II include spontaneous breathing over the ventilator, minimal blood loss, and hypothermia

4. Materials and Methods:

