4.4 Definitions

- *Bolus* – 10 - 20 ml/kg fluid (isotonic crystalloid, colloid, or blood product) up to 1 L and given within a 10 minutes period
- *Fluid responders* – Children who have a pre- and post-fluid challenge $\Delta VPeak > 10\%$ calculated using the equation ($\Delta VPeak_{pre} = (VPeakmax_{pre} - VPeakmin_{pre}) /$

Protocol #: 18-2513

PI: [name]

Version date: 07/01/2019

$$[(V_{peakmean_{pre}})] - (\Delta V_{Peak_{post}} = (V_{Peakmax_{post}} - V_{Peakmin_{post}}) / [(V_{peakmean_{post}})] \times 100$$

- *Multiple fluid challenges* – If more than one fluid bolus is administered at least 30 minutes apart, they will be reported as individual events
- *Pre-bolus measurements* – Hemodynamic measurements will be calculated or recorded three times thirty seconds apart and averaged just before a bolus is administered. Cine loops from IVC measurements will be recorded three times, thirty seconds apart for post-hoc CI calculation. Peak aortic velocity and CRI will be recorded on the EDM monitor and averaged over 90 seconds.
- *Post-bolus measurements* - Hemodynamic measurements will be calculated or recorded three times and averaged five minutes after a bolus is completed. These measurements will be time and repeated in an identical fashion to pre-bolus measurements.

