4.8 Data Analysis

Protocol #: 18-2513

PI: [name]

Version date: 07/01/2019

Univariate comparisons between various measures will be compared between the fluid responder and non-responder groups using t-tests or Fisher's exact test for continuous and categorical measures, respectively. Area under the curve will be calculated for CI and CRI using both simple logistic regression models including no confounders and multiple logistic regression models including confounders. Confounders will be identified for inclusion in the multiple logistic regression models by calculating the univariate association with the gold standard (using a $p < 0.10$ threshold). These adjusted models will be used to verify thresholds for classification using CI and CRI which will then be applied to calculate classification summary measures (e.g., PPV, NPV, sensitivity, and specificity). Data analysis will be performed by a biostatistician funded by the Division of Pediatric Surgery using R and SAS statistical software programs.

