4.9.2 CardioQ-EDM Contraindications

- Doppler probes (DP240 and I2n) should not be placed in patients under 16 years of age. We will be using the KDP72 probe
- Do not use where nasal injuries are apparent or may have occurred.
- Do not use where nasal polyps exist.
- Do not use where there are circumstances of facial trauma.
- Do not use where there is a risk of brain injury.
- Do not use in patients undergoing intra-aortic balloon pumping.
- Do not use with carcinoma of the pharynx, larynx or esophagus.
- Do not use with aneurysms of the thoracic aorta.
- Do not use with tissue necrosis of the esophagus or nasal passage.
- Do not use in close proximity to laser surgery.
- Do not use in patients with pharyngo-oesophago-gastric pathology and/or severe bleeding diatheses.

5. Specific Aims:

Aim I: Define fluid responders based on aortic ΔV_{peak} : Among infants undergoing cranial vault reconstruction for craniosynostosis, we aim to determine the proportion who respond to clinically administered fluid or blood products defined by pre- and post-fluid challenge EDM $\Delta V_{Peak} >10\%$.

Mock-up Table 1: Demographics of Responders and Non-Responders to Initial 10 mL/kg bolus prior to surgical incision

Variable	Responders	Non-Responders	P-value
Demographics			
Age			
Weight			
Height			
BMI			
Gender			
Ethnicity			
Duration of NPO status			
Associated syndrome			

Legend: BMI, body mass index; npo, nil per os

Aim II: Calculate the PPV, NPV, sensitivity, specificity, and optimal threshold for CRI and collapsibility index as tools to prediction fluid responder

Protocol #: 18-2513

PI: [name]

[figure not shown]
Version date: 07/01/2019

		Fluid Responsive	
		Yes	No
CRI Threshold	+	True Positive	False Positive
	-	False Negative	True Negative

		Fluid Responsive	
		Yes	No
CI Threshold ($\geq 15\%$)	+	True Positive	False Positive
	-	False Negative	True Negative

Performance will also be calculated for heart rate, systolic blood pressure, mean arterial pressure, pulse pressure variability and stroke volume variability. Two separate analyses will be performed – one for the 10 ml/kg protocolized bolus provided immediately after induction and one accounting for all boluses provided.

Mock-up Figure

Mock-up Table 2 – Performance at predicting fluid responsiveness

Variable	Correlation (r)	AUC
IVC CI		
CRI		
SBP		
PPV		
SVV		
MAP		
HR		

Protocol #: 18-2513

PI: [name]

Version date: 07/01/2019

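### CRI and IVC CI are to be compared with current indices, but the readable plan evaluates each index on its own, with no AUC interval and no between-index difference

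*Combined protocol and SAP*

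**What the plan says.** The study-goal paragraph promises a comparison: "we will compare the predictive utility of non-invasive devices such as the CipherOx-CRI and IVC CI to currently employed indices". It lists the comparators as "currently employed indices (heart rate, systolic blood pressure, urine output and pulse pressure variability" and then states what hangs on the result: "If the CipherOx-CRI or IVC CI proved to be as predictive or better at predicting fluid responders, we hope to replace invasive arterial lines". Hypothesis II in section 3 is comparative too. It expects an AUROC of about 0.9 for CRI and the collapsibility index, "while other indices will have a lower predictive accuracy".

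The analysis text is narrower:

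- Section 4.8: "Area under the curve will be calculated for CI and CRI using both simple logistic regression models including no confounders", and also from models with confounders. Thresholds and classification measures follow. The only tests named there (t-test and Fisher's exact) compare responders with non-responders on one measure at a time.
- Section 5, Aim II: "Performance will also be calculated for heart rate, systolic blood pressure, mean arterial pressure, pulse pressure variability and stroke volume variability". There are to be two analyses, "one for the 10 ml/kg protocolized bolus provided immediately after induction and one accounting for all boluses provided".
- Mock-up Table 2: one row per index (IVC CI, CRI, SBP, pulse pressure variability, SVV, MAP, HR), with one correlation and one AUC.
- Section 4.4, on repeat boluses: "If more than one fluid bolus is administered at least 30 minutes apart, they will be reported as individual events".

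**The concern.** A statement that one index predicts as well as another, or better, is about a difference. The planned outputs describe each index singly and give no measure of uncertainty for that difference. Someone following the plan would place seven AUCs in a column and read off the order. In a study of a few dozen infants, that order can put a less accurate device level or ahead by chance, and the reader would have no interval to show it. There are two devices, and the goal is met if either succeeds, so there are two chances of this. At stake is the support for the suggestion that a non-invasive device could stand in for arterial-line monitoring.

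**Working it through.** **1. Is a between-index analysis planned anywhere?** The study goal and Hypothesis II call for one. Section 4.8, Aim II (sections 3 and 5) and mock-up Table 2 provide r, AUC, sensitivity, specificity, predictive values and thresholds, all per index. No AUC interval, paired difference or margin appears. The plan therefore has no figure of its own to reproduce.

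**2. Inputs.**
- From the documents: AUROC about 0.9 for the devices (Hypothesis II); about half the infants responding to the first bolus (Hypothesis Ia); 30 probes (section 4.2); 50-70 cases a year (study-goal section).
- Assumed: N = 30 or 50-70 (supply and caseload figures, not a stated sample size); comparator AUC; within-group correlation between indices 0.2-0.5; two-sided 5% level.

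**3. Analytic check, 15 responders and 15 non-responders.** The Hanley-McNeil variance is [A(1-A) + (m-1)(Q1-A²) + (n-1)(Q2-A²)]/(mn), with Q1 = A/(2-A) and Q2 = 2A²/(1+A).
- A = 0.90: [0.09 + 14(0.00818 + 0.04263)]/225 = 0.00356, so SE = 0.060. The 95% interval is about 0.78 to 1.00 (upper limit truncated).
- A = 0.80: [0.16 + 14(0.02667 + 0.07111)]/225 = 0.00680, so SE = 0.082.
- Paired SE = √(SE1² + SE2² - 2r·SE1·SE2), where r is the correlation between the two AUC estimates. With r = 0.5: √(0.00356 + 0.00680 - 0.00492) = 0.074. The interval for a true difference of 0.10 is 0.10 ± 1.96 × 0.074, or -0.05 to 0.25, and power is 27%. With r = 0.3 power is 21%; with r = 0.7 it is 40%.

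**4. Simulation.** Binormal indices, two devices and one comparator, equal groups, group separation √2·Φ⁻¹(AUC), paired DeLong intervals, thousands of trials per setting. A repeat run agreed within simulation error.

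| True AUC, device v comparator | Result | N = 30 | N = 50-70 |
|---|---|---|---|
| 0.75 v 0.85 | one device level or ahead | 12-18% | 4-11% |
| | at least one of two | 21-29% | 6-18% |
| | 95% half-width of difference | 0.17-0.21 | 0.11-0.16 |
| 0.80 v 0.85 | one device level or ahead | 27-31% | 17-26% |
| | at least one of two | 43-46% | 27-39% |
| 0.90 v 0.80 | 95% interval excludes 0 (one device) | 16-21% | 29-53% |

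For 0.90 v 0.80, ranking puts a given device level or ahead in about 87-98% of trials across these sizes. With one third responders, the 0.75 v 0.85 figures barely move (14-18% and 4-11%).

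**5. Repeat boluses.** Assume 30 or 60 children, 2-3 boluses each, and child-level correlation 0.3-0.6. An interval for the AUC difference that treats boluses as independent then covers the truth in 88-95% of trials. A bootstrap that resamples children covers it in 93-95%.

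**The case against.** The strongest reply is that this is a small estimation study. Aim II asks for accuracy per index, and replacing arterial lines is worded as a hope, not a decision rule. If Hypothesis II is right, ranking will usually give the right order. This stands, and it limits the seriousness of the point. It does not remove it, because the goal paragraph commits to a comparison and Hypothesis II predicts its direction.

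Three further replies have some force. First, a reader might infer that AUCs are the only planned output. They are not: correlations, thresholds and classification measures are planned too, though also one index at a time. Second, a reader might infer that no interval is planned anywhere. Only the readable text can be judged: the mock-up figure under Aim II is not shown, and some parts of the document were not available. A figure might carry intervals, though it is unlikely to define a paired contrast. Third, section 4.6 says fluid is not to wait for study measurements, so some pre-bolus readings may be missing and pairing may be incomplete. The fix has to allow for that.

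**Conclusion.** The point holds as a gap between a stated comparison and an analysis that does not make it. It should be corrected, but it does not undermine the study.

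A reader might infer that ranking would often mislead. The figures do not support that in general: about 4-18% for a deficit of 0.10, rising to about 17-31% for a deficit of 0.05, and higher when either of two equally inferior devices may count. The true AUCs are unknown, and both of those scenarios run against Hypothesis II. In the hypothesised direction the order is usually right, but it would seldom be demonstrated at 30 infants and only about a third to a half of the time at 50-70. Nor do the documents state a formal non-inferiority claim, and the lack of a visible sample size is not counted against the plan. All sizes rest on the assumed N, correlation, responder share and comparator AUC. That ranked point estimates carry no uncertainty for the difference does not depend on them.

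**What to change.** In section 4.8 and Aim II, add the unadjusted paired AUC difference with a 95% interval for CRI and for IVC CI, each minus each current index in mock-up Table 2 (SBP, pulse pressure variability, SVV, MAP, HR). Unadjusted matters because section 4.8 names confounder-adjusted AUCs only for CI and CRI, and those are not like for like with a current index's unadjusted AUC. Compute each difference on boluses where both indices were recorded, and report the number of pairs. Use DeLong for the induction bolus and a child-level bootstrap for the all-bolus analysis.

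Base any claim of better or equal prediction on the interval, not on rank. Pulse pressure variability is the natural key comparator, because it is the index in the goal paragraph's list that section 4.6.5 takes only from the arterial line by definition of the waveform. Any margin for equal prediction is the sponsor's choice, fixed before analysis. A margin is no cure-all. At 0.80 v 0.85, N = 70 and correlation 0.5, a margin of -0.10 passes the inferior device in 18% of trials, against 17% by ranking. A margin of -0.05 passes it in 3%, but passes a truly equal device in only 15-19%.

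The cost is a little more analysis on data section 4.6.5 already collects, and a real chance of an inconclusive answer.

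Secondary: urine output is a named comparator in the goal paragraph but is absent from Aim II, the section 4.6.5 parameter list and mock-up Table 2. Reconcile these, either by adding it (which needs a data field) or by saying why it is not compared.

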While numerous tools are available to guide resuscitation, one potential benefit of this project is to validate the use of CipherOx-CRI in this cohort. If CRI proves to be a valuable predictor of intravascular volume status and the need for volume expansion, this could negate the need for arterial line placement which is time consuming, invasive, and associated with complications such as arterial thrombosis. Furthermore, after validation in this cohort, additional studies could be performed in other groups of children at risk for hemorrhagic shock in the hopes to guide ongoing resuscitation accurately without the need for invasive devices.

3. Specific Aims and Hypotheses:

Aim I: Among infants undergoing cranial vault reconstruction for craniosynostosis, we aim to determine the proportion who respond to clinically administered fluid or blood products defined by pre- and post-fluid challenge $\Delta V_{Peak} > 10\%$.

Hypothesis Ia: We hypothesize that approximately half of the cohort will be fluid responsive defined by ΔV_{Peak} by $> 10\%$ after a 10 mL/kg fluid bolus is administered immediately following induction. Although this is a prediction, it is based on previous published reports suggesting a relatively even distribution among patients who clinicians believe need volume expansion. Additionally, because these children have a mean weight of 6.4 kg and will have been nil per os for several hours prior to surgery, they are at risk for intravascular volume depletion even prior to blood loss.

Hypothesis Ib: Because clinicians use pulse pressure variability, heart rate, systolic blood pressure, urine output, and blood loss to gauge need for ongoing resuscitation (either crystalloid, colloid, or blood), we suspect that more than half of subsequent fluid challenges will be given to infants who are fluid responsive (defined by a pre- and post-bolus ΔV_{Peak} of $> 10\%$).

Aim II: To determine the PPV, NPV, sensitivity, specificity, and optimal threshold for CRI, collapsibility index, pulse pressure variability, stroke volume variability, heart rate, systolic blood pressure, and mean arterial pressure as tools to predict fluid responsiveness using pre- and post-fluid challenge $\Delta V_{Peak} > 10\%$ to define fluid responders.

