4.5 Decision for volume expansion

All children receive a 10 ml/kg crystalloid bolus immediately after induction. The need/decision for a fluid bolus will be determined by the anesthesiologist based on clinical judgement. Currently, the anesthesiologist places an arterial line at the beginning of the case and using pulse pressure variability, HR, SBP, MAP, urine output, and blood loss determines whether or not a fluid or blood bolus is appropriate. Data collected from the CardioQ-EDM, CipherOx-CRI, and bedside ultrasound will not be provided to the care team.

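### No comparator, bolus set or CRI/CI rule is named as decisive for the arterial-line statement, so the supporting comparison could be chosen after the results are seen

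*Combined protocol and SAP*

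**What the plan says.** Three places link CRI or CI performance to a conclusion.

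- **Introduction, goal of the study:** "If the CipherOx-CRI or IVC CI proved to be as predictive or better at predicting fluid responders, we hope to replace invasive arterial lines". Either index would do.
- **Last paragraph before section 3, on dispensing with arterial lines:** "If CRI proves to be a valuable predictor of intravascular volume status and the need for volume expansion, this could negate the need for arterial". Only CRI is mentioned, and no comparator.
- **Section 3, Hypothesis II:** "CRI and collapsibility index will reliably predict fluid responsive patients with an approximate area under the receiver operating characteristic curve (AUROC) of 0.9", with the other indices expected to be lower. Both indices are expected to do well.

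Three places list the indices to be matched or now in use.

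- **Introduction:** "currently employed indices (heart rate, systolic blood pressure, urine output and pulse pressure variability".
- **Section 3, Aim II:** "pulse pressure variability, stroke volume variability, heart rate, systolic blood pressure, and mean arterial pressure as tools to predict fluid responsiveness", alongside CRI and CI.
- **Section 4.5, current practice:** the anesthesiologist, "using pulse pressure variability, HR, SBP, MAP, urine output, and blood loss determines whether or not a fluid or blood bolus is appropriate".

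Section 5, Aim II, adds: "Two separate analyses will be performed – one for the 10 ml/kg protocolized bolus provided immediately after induction and one accounting for all boluses provided". Neither analysis is called primary.

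Section 4.8 calculates AUCs for CI and CRI, with and without confounders, and compares responders with non-responders by t-tests or Fisher's exact test. It gives no comparison of two AUCs, no margin, no test alpha and no multiplicity rule. Its only p-value threshold (0.10) is for confounder screening.

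**The concern.** The introduction promises a comparison of new with current indices and attaches a practical consequence to it, but the analysis section does not say how that comparison is made or read. Three choices stay open until the data are in: which new index, which comparator and which bolus set. The three statements can also diverge on the same data. If CRI does well and CI does not, the introduction and the closing background paragraph are satisfied, but Hypothesis II is not. If CI does well and CRI does not, only the introduction is satisfied.

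At stake is a suggestion to give up arterial lines in infants having cranial surgery. If the most favourable of several comparisons may carry it, it can be made when both new indices are in truth less accurate than the arterial-line index they would replace.

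**Working it through.** The available text states no sample size, alpha or margin, so there is no figure of the plan's to reproduce.

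**1. Comparator lists side by side**

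| Index | Introduction | Aim II | Section 4.5 |
|---|---|---|---|
| HR | yes | yes | yes |
| SBP | yes | yes | yes |
| PPV | yes | yes | yes |
| MAP | no | yes | yes |
| SVV | no | yes | no |
| Urine output | yes | no | yes |
| Blood loss | no | no | yes |

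HR, SBP and PPV are in all three. Of these, the protocol's Table 2 places only PPV under arterial lines; HR and SBP are under non-invasive vital signs.

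**2. Number of possible contrasts**

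2 new indices × 5 Aim II comparators × 2 bolus sets = 20. With only the three shared comparators, 2 × 3 × 2 = 12.

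**3. If each contrast were tested**

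Assume two-sided 0.05, so 0.025 in the direction favouring CRI or CI. If independent, the chance of at least one falsely favourable result is 1 − 0.975^20 = 0.40 for 20 contrasts and 1 − 0.975^12 = 0.26 for 12. The contrasts share data, so I also used equally correlated normal statistics (200,000 draws). For 20 contrasts this gives 0.21 at correlation 0.5 and 0.11 at 0.8, hence about 21% (11-40%).

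**4. If point estimates are read instead**

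With no margin stated, this reading is open. Inputs:

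- 30 children: the probe supply in section 4.2, not a stated sample size.
- Half responders: Hypothesis Ia.
- Assumed: one extra bolus per child, within-child correlation 0.5, true AUC 0.70 for CRI and CI and 0.80 for PPV.

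Each index is normal, shifted in responders by √2 × Φ⁻¹(AUC): 0.74 for AUC 0.70 and 1.19 for AUC 0.80. Results from 4,000 simulated trials per row:

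| Correlation between indices | CRI ≥ PPV, first bolus | CRI or CI ≥ PPV, first bolus | CRI or CI ≥ PPV, either set |
|---|---|---|---|
| 0 | 22% | 35% | 40% |
| 0.3 | 18% | 28% | 32% |
| 0.5 | 15% | 25% | 28% |

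A separately coded simulation gave 16-24% for the first result column and 29-43% for the last, so I quote 15-24% and 28-43%. Most of the rise comes from allowing either index; the second bolus set adds 3 to 5 points.

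In the runs tabulated, CRI and CI disagree on passing in 19-25%, and the two bolus sets disagree for CRI in 13-17%. If three or five comparators all have true AUC 0.80, the direction in Hypothesis II (both new indices at or above every comparator, first bolus) holds in only 0.1-1.2%.

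The size depends on the assumed gap. With 0.75 against 0.80, the one-contrast and either/either rates are 30-36% and 53-60%. With 0.70 against 0.85, they are 5-11% and 10-21%.

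**5. Selection of later boluses**

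Section 4.5 says PPV, HR, SBP and MAP help decide whether a bolus is given, so later boluses are selected on the comparators. As an illustration, take a PPV index with true AUC 0.80 and half responders, and keep only events above a PPV cut-off. Its AUC falls to 0.73 if the lowest 30% are removed, 0.71 for 40% and 0.69 for 50%. CRI and CI are affected only so far as they correlate with PPV. Section 4.7 says the initial bolus is given whatever the indices show, so it escapes this.

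**6. Precision of one named contrast**

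By the Hanley-McNeil formula, an AUC of 0.80 with 15 responders and 15 non-responders has SE 0.082. The 95% half-width for a difference of two such AUCs is 1.96 × √(2 × 0.082² × (1 − r)): 0.23 at r = 0 and 0.16 at r = 0.5. With an assumed margin of 0.10, one-sided 0.025 and true AUCs of 0.8 to 0.9, power for non-inferiority at 30 children is 0.14-0.39.

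**The case against.** The strongest reply is that nothing here is a decision rule. The introduction expresses a hope, the closing background paragraph describes a possible benefit and foresees further studies, and Hypothesis II is an expectation. A reader might infer three competing formal success criteria; the documents do not support that. Nor are the current indices unspecified: the introduction names four. What remains is that none is singled out, and that the only practical use the goal describes has no fixed basis.

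Two larger numbers are tempting and should not be used. Counting both tails, 20 contrasts give about 42% (23-64%), but half of that is CRI or CI appearing worse, which cannot produce a chance winner. And if heart rate, say, has a true AUC of 0.60, CRI or CI at 0.70 will match or beat it in over 99% of trials. That is a true difference, not an error, and no section says that beating the weakest index justifies dropping arterial lines.

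Three objections to the remedy stand in part:

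- The initial bolus precedes incision, whereas the background calls for validation in children with significant blood loss.
- SVV, SBP and MAP are also taken from the arterial line (section 4.6.5), so matching PPV alone would not settle replacement.
- A rule that CI may be tested only if CRI succeeds would be a preference; the documents do not require it.

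Finally, the opening of the document and part of the introduction were not available. Absence is shown only for the remaining text.

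**Conclusion.** The concern holds in this form: the text available lists the current indices but names no comparator, bolus set or CRI/CI rule as decisive for the arterial-line statement, and section 4.8 plans no AUC-versus-AUC comparison.

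Under the stated assumptions, leaving index and bolus set open raises the chance of a misleading point estimate against PPV from about 15-24% to about 28-43%. If 20 contrasts were formally tested, the chance of at least one falsely favourable result would be about 21% (11-40%). The AUCs, correlations, extra bolus, alpha and use of the probe count as sample size are assumptions, not the plan's figures. The tilt against PPV in the all-bolus set is a possibility shown by illustration; its size here is unknown.

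This should be corrected before analysis. It does not invalidate the data collection. Naming one contrast does not remove the risk either, because 15-24% remains if point estimates alone are read. A confidence interval and a stated margin are therefore part of the correction.

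**What to change.** In section 4.8 and in Aim II (sections 3 and 5):

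1. Make the protocolized post-induction bolus the primary analysis set. It gives one event per child and does not depend on the indices.
2. Name PPV as the deciding comparator for any arterial-line statement.
3. Report the paired difference in index-only AUC with a 95% confidence interval: CRI minus PPV as the primary contrast, CI minus PPV as secondary under a stated multiplicity rule.
4. State beforehand what difference counts as equally predictive.
5. Label the all-bolus analysis and the HR, SBP, MAP and SVV comparisons exploratory.
6. Align the goal paragraph, the closing background paragraph and Hypothesis II with this contrast, and reconcile the comparator lists, including urine output.

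This changes wording and analysis only; it needs no new measurements. It has costs that the plan should state. The primary result will cover only the setting before incision and surgical blood loss. The all-bolus results cannot support the arterial-line statement alone. With about 30 children, a half-width of roughly 0.16-0.23 in the AUC difference is too wide to establish equivalence, so the result should be presented as estimation. Confirming a margin of 0.10 with 80% power would need about 82-310 children under the assumptions in step 6 of the working, with r between 0 and 0.5.
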